### 8.1.3 CLASSIFICATION OF AN ADVERSE EVENT

---

#### 8.1.3.1 SEVERITY OF EVENT

For adverse events (AEs) not included in the protocol defined grading system, the following guidelines will be used to describe severity.

- **Mild** – Events require minimal or no treatment and do not interfere with the participant's daily activities.
- **Moderate** – Events result in a low level of inconvenience or concern with the therapeutic measures. Moderate events may cause some interference with functioning.
- **Severe** – Events interrupt a participant's usual daily activity and may require systemic drug therapy or other treatment. Severe events are usually potentially life-threatening or incapacitating. Of note, the term "severe" does not necessarily equate to "serious".]

---

#### 8.1.3.2 RELATIONSHIP TO STUDY INTERVENTION

All adverse events (AEs) must have their relationship to study intervention assessed by the investigator who examines and evaluates the participant based on temporal relationship and his/her clinical judgment. The degree of certainty about causality will be graded using the categories below.

- **Related** – The AE is known to occur with the study intervention, there is a reasonable possibility that the study intervention caused the AE, or there is a temporal relationship between the study intervention and event. Reasonable possibility means that there is evidence to suggest a causal relationship between the study intervention and the AE.
- **Not Related** – There is not a reasonable possibility that the administration of the study intervention caused the event, there is no temporal relationship between the study intervention and event onset, or an alternate etiology has been established.

### 8.1.3.3 EXPECTEDNESS

The principal investigator in consultation with the sponsor will be responsible for determining whether an adverse event (AE) is expected or unexpected. An AE will be considered unexpected if the nature, severity, or frequency of the event is not consistent with the risk information previously described for the study intervention.

### 8.1.4 TIME PERIOD AND FREQUENCY FOR EVENT ASSESSMENT AND FOLLOW-UP

The occurrence of an adverse event (AE) or serious adverse event (SAE) may come to the attention of study personnel during study visits and interviews of a study participant presenting for medical care, or upon review by a study monitor.

All AEs including local and systemic reactions not meeting the criteria for SAEs will be captured on the appropriate case report form (CRF). Information to be collected includes event description, time of onset, investigator assessment of severity, relationship to study product (assessed only by those with the training and authority to make a diagnosis), and time of resolution/stabilization of the event. All AEs occurring while on study must be documented appropriately regardless of relationship. All AEs will be followed to adequate resolution.

Any medical condition that is present at the time that the participant is screened will be considered as baseline and not reported as an AE. However, if the study participant's condition deteriorates at any time during the study, it will be recorded as an AE.

Changes in the severity of an AE will be documented to allow an assessment of the duration of the event at each level of severity to be performed. AEs characterized as intermittent require documentation of onset and duration of each episode.

Study team will record all reportable events with start dates occurring any time after informed consent is obtained until 7 (for non-serious AEs) or 30 days (for SAEs) after the last day of study participation. At each study visit, the investigator will inquire about the occurrence of AE/SAEs since the last visit. Events will be followed for outcome information until resolution or stabilization.

### 8.1.5 ADVERSE EVENT REPORTING

Any adverse experience that occurs in this study that is serious, unexpected, and related or probably related to the study design must be reported to the IRB of record within 10 working days after the investigator first receives a report of the event by completing and submitting an adverse event report form as per IRB of record policy and procedures.

Any unanticipated adverse device effects must be reported to the IRB within 10 working days after the investigator first learns of the event by completing and submitting an adverse event report for as per IRB of record policy and procedures.

All adverse events that do not meet the above reporting requirements should be summarized and provided to the IRB at the time of continuing review.

---

#### 8.1.6 SERIOUS ADVERSE EVENT REPORTING

The study investigator will immediately, but no longer than within 5 working days after investigator first becomes aware of the event, report to the sponsor any serious adverse event, whether or not considered study intervention related, including those listed in the protocol or investigator brochure and must include an assessment of whether there is a reasonable possibility that the study intervention caused the event. Study endpoints that are serious adverse events must be reported in accordance with the protocol unless there is evidence suggesting a causal relationship between the study intervention and the event. In that case, the investigator must immediately report the event to the sponsor.

The study investigator shall complete an Unanticipated Adverse Device Effect Form and submit to the study sponsor and to the reviewing Institutional Review Board (IRB) as soon as possible, but in no event later than 5 working days after the investigator first learns of the effect. The study sponsor is responsible for conducting an evaluation of an unanticipated adverse device effect and shall report the results of such evaluation to the Food and Drug Administration (FDA) and to all reviewing IRBs and participating investigators within 10 working days after the sponsor first receives notice of the effect. Thereafter, the sponsor shall submit such additional reports concerning the effect as FDA requests.

All serious adverse events (SAEs) will be followed until satisfactory resolution or until the site investigator deems the event to be chronic or the participant is stable. Other supporting documentation of the event may be requested by the Data Coordinating Center (DCC)/study sponsor and should be provided as soon as possible.

The study sponsor will be responsible for notifying the Food and Drug Administration (FDA) of any unexpected fatal or life-threatening suspected adverse reaction as soon as possible, but in no case later than 7 calendar days after the sponsor's initial receipt of the information. In addition, the sponsor must notify FDA and all participating investigators as soon as possible, but in no case later than 15 calendar days after the sponsor determines that the information qualifies for reporting.

---

#### 8.1.7 REPORTING EVENTS TO PARTICIPANTS

Not applicable.

#### 8.1.8 EVENTS OF SPECIAL INTEREST

Not applicable.

#### 8.1.9 REPORTING OF PREGNANCY

If a female patient becomes pregnant while participating in this study and receiving DAPT, a pregnancy report form should be completed and expeditiously submitted to the sponsor to facilitate outcome follow-up. Information on the status of the mother and child will be forwarded to the sponsor. Generally, follow-up will be no longer than 6-8 weeks following the estimated delivery date. Any premature termination of the pregnancy will be reported.

While pregnancy itself is not considered to be an AE or SAE, any pregnancy complication will be recorded as an AE or SAE.

## 8.2 UNANTICIPATED PROBLEMS

#### 8.2.1 DEFINITION OF UNANTICIPATED PROBLEMS (UP)

The Office for Human Research Protections (OHRP) considers unanticipated problems involving risks to participants or others to include, in general, any incident, experience, or outcome that meets all of the following criteria:

- Unexpected in terms of nature, severity, or frequency given (a) the research procedures that are described in the protocol-related documents, such as the Institutional Review Board (IRB)-approved research protocol and informed consent document; and (b) the characteristics of the participant population being studied;
- Related or possibly related to participation in the research (“possibly related” means there is a reasonable possibility that the incident, experience, or outcome may have been caused by the procedures involved in the research); and
- Suggests that the research places participants or others at a greater risk of harm (including physical, psychological, economic, or social harm) than was previously known or recognized.

This definition could include an unanticipated adverse device effect, any serious adverse effect on health or safety or any life-threatening problem or death caused by, or associated with, a device, if that effect, problem, or death was not previously identified in nature, severity, or degree of incidence in the investigational plan or application (including a supplementary plan or application), or any other unanticipated serious problem associated with a device that relates to the rights, safety, or welfare of subjects (21 CFR 812.3(s)).

## 8.2.2 UNANTICIPATED PROBLEM REPORTING

The investigator will report unanticipated problems (UPs) to the reviewing Institutional Review Board (IRB) and to the Data Coordinating Center (DCC)/lead principal investigator (PI). The UP report will include the following information:

- Protocol identifying information: protocol title and number, PI's name, and the IRB project number;
- A detailed description of the event, incident, experience, or outcome;
- An explanation of the basis for determining that the event, incident, experience, or outcome represents an UP;
- A description of any changes to the protocol or other corrective actions that have been taken or are proposed in response to the UP.

To satisfy the requirement for prompt reporting, UPs will be reported using the following timeline:

- UPs that are serious adverse events (SAEs) will be reported to the IRB and to the DCC/study sponsor within 5 working days of the investigator becoming aware of the event.
- Any other UP will be reported to the IRB and to the DCC/study sponsor within 10 working days of the investigator becoming aware of the problem.

An investigator shall submit to the sponsor and to the reviewing Institutional Review Board (IRB) a report of any unanticipated adverse device effect occurring during an investigation as soon as possible, but in no event later than 10 working days after the investigator first learns of the effect (21 CFR 812.150(a)(1)). A sponsor who conducts an evaluation of an unanticipated adverse device effect under 812.46(b) shall report the results of such evaluation to the Food and Drug Administration (FDA) and to all reviewing IRB's and participating investigators within 10 working days after the sponsor first receives notice of the effect. Thereafter the sponsor shall submit such additional reports concerning the effect as FDA requests (21 CFR 812.150(b) (1)).

## 8.2.3 REPORTING UNANTICIPATED PROBLEMS TO PARTICIPANTS

Unanticipated problems that are determined to be related or probably related to the study intervention will be shared with the patients at the following visit after informed consent approved by IRB of record.

## 9 STATISTICAL CONSIDERATIONS

### 9.1 STATISTICAL HYPOTHESES

Outcome measures include 1-13 month post-procedure rates of cardiac death and myocardial infarction. This single-arm prospective design will compare rates on the dependent variables following

Boston Scientific IVUS-guided SYNERGY™ Stent implantations with standard of care rates in the target population. The null and alternative hypotheses are as follows:

$$H_0 = p = p_0$$

The null hypothesis states that there is no difference on myocardial infarction or cardiac death rates.

$$H_1: p < p_0$$

## 9.2 THE ALTERNATIVE HYPOTHESIS STATES THAT PATIENTS UNDERGOING SYNIVUS-DAPT TREATMENT WILL HAVE LOWER RATES OF MYOCARDIAL INFARCTION OR CARDIAC DEATH. SAMPLE SIZE DETERMINATION

An a priori power analysis was conducted for a one-sample binomial test with an alpha of .05 (one-tailed), beta of .05, constant proportion ( $p$ ) of .031, and assumed primary endpoint proportion of 0.0047 resulting in a needed sample size of 231.

The consideration of historical data on timing and incidence of myocardial infarction and stent thrombosis from published meta-analysis and related literature, the SCAAR registry and ACS subsets (De Luca, Dirksen, Spaulding, et al, 2012; Ellis, Colombo, Grube, et al, 2007; Palmerini, Biondi-Zocca, Riva, et al, 2012; Palmerini, Kirtane, Serruys, et al, 2012; SCAAR registry and ACS subset, 2016). Historic rates at 1-year follow up for ST showed variability ranging from 0.3 to 5.3%. Rates of MI range from 1.9 to 8.8%. A time-to-event bivariate exponential distribution function was used to determine criteria for sample sizes based on a 95% power determination resulting in a historic rate determination of 3.1%. Patients lost to follow-up will not be included in the final analysis, and additional patients will be recruited for study participation to reach the needed sample of 231.

The FDA has approved an initial phase of the investigation for 100 U.S patients. Accordingly, the sample size of N=100 for the initial phase is not statically based. Should approvals for study continuation be granted, the total sample size for subsequent phases will remain at 231, inclusive of subjects enrolled on this initial phase.

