## 1 PROTOCOL SUMMARY

### 1.1 SYNOPSIS

Title:	SYNERGY™ Stent System Implantation with mandatory Intra-Vascular Ultra-Sound Guidance to Examine the Safety of Cessation of Dual Anti-Platelet Therapy in High Bleeding Risk Patients One Month (SYNIVUS-DAPT)
Study Description:	This is a prospective multicenter single-arm study designed to characterize the safety of 1 month of dual antiplatelet therapy (DAPT) in a patient population who are at increased risk for bleeding who are undergoing iLab IVUS-guided percutaneous coronary intervention (PCI) with a SYNERGY Everolimus-Eluting Platinum Chromium Coronary Stent System (SYNERGY™ Stent System). We hypothesize that the 1 to 13 month rates of Cardiac Death or Myocardial Infarction (SCAI definition), and Stent thrombosis after Boston Scientific IVUS-guided SYNERGY™ Stents implantation will be low and provide key hypothesis generating information to inform future larger-scale clinical studies
Objectives:	Primary Objectives: To determine the safety of 1-month DAPT in a High Bleeding Risk (HBR) patient population who are undergoing SYNERGY™ stent implantation.
Endpoints:	Primary Endpoint: 

• Rate of cardiac death or myocardial infarction (SCAI definition) from 1 to 13 months post-index procedure in the “as treated” (eligible for 30 day DAPT cessation) population.

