#### 9.4.2 ANALYSIS OF THE PRIMARY ENDPOINT

*For primary endpoints:*

Prevalence rates of cardiac death and myocardial infarction will be determined for the sample. The binomial test will be conducted to test the significance of deviations from the expected distribution of observations dichotomized as “*did not occur*” or as “*occurrence*” for each outcome.

*For safety endpoints:*

Prevalence rates for safety outcomes including ischemia-driven (ID) target lesion revascularization, ID target vessel revascularization, target lesion failure, target vessel failure, all-cause death, and myocardial infarction will be evaluated with binomial tests.

The test formula to be used is as follows:

$$P(X) = C^n_k \ p^k (1-p)^{n-k}$$

All data will be screened for non-parametric statistical test assumptions. Accordingly, all dichotomous outcomes will be screened for exclusivity and appropriateness for inclusion in data analysis. Missing data, nonadherence and data lost to follow-up will be excluded from the final analysis.

The a priori alpha level for all statistical tests will be set at .05. To adjust for a potentially inflated family-wise error rate, the Bonferroni correction ( $\alpha/m$ ) will be applied for multiple tests with the same sample.

---

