#### 9.4.4 PLANNED INTERIM ANALYSES

A 7 month planned interim analysis for the first 50 patients enrolled using the O'Brien-Fleming method will be conducted for cardiac death or myocardial infarction rate. Using an a priori alpha of .05, the adjusted alpha for the interim analysis will be 0.0054 and 0.0492 for the final analysis for consideration of frequency rates and obtained p-values at each analysis time point. Interim analysis outcomes will be used to assess trial efficacy, early evidence of harm, and safety to inform futility determinations and continuation considerations. Frequency rates on each outcome variable that exceed the non-inferiority margin of  $\pm 5\%$  for the interim analysis will result in temporary halting for further safety evaluations. The project statistician will conduct the planned interim analysis results will be reviewed by the study PI and research team.

---

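### At N=231 the planned binomial test has 90.4% power, not the stated 95%, and the plan gives no rejection count

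*Combined protocol and SAP*

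**What the plan says.** Section 9.1 sets a one-sided alternative, with the event rate below the reference rate. Section 9.2 describes a "one-sample binomial test with an alpha of .05 (one-tailed), beta of .05, constant proportion" of .031, and an "assumed primary endpoint proportion of 0.0047 resulting in a needed sample size of 231". The 95% figure is repeated in its second paragraph: "A time-to-event bivariate exponential distribution function was used to determine criteria for sample sizes based on a 95% power determination".

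For the analysis, section 9.4.2 says: "The binomial test will be conducted to test the significance of deviations from the expected distribution of observations". It prints the binomial probability of k events in n as the test formula, sets alpha at .05, and adds a Bonferroni correction that "will be applied for multiple tests with the same sample". It gives no number of tests and does not say whether the primary test is included.

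Section 9.4.4 changes the threshold because of the interim look: "the adjusted alpha for the interim analysis will be 0.0054 and 0.0492 for the final analysis".

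The synopsis (1.1) places the primary endpoint in the as-treated group, glossed there as "eligible for 30 day DAPT cessation) population". No section states how many events, out of 231 or any other number, would lead to rejection of the null hypothesis.

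**The concern.** The sizing method and the test do not match. With a null rate of 3.1% and an assumed rate of 0.47%, about 7.2 events are expected in 231 patients under the null and 1.1 under the alternative. At counts this low a binomial test moves in large steps, and a smooth approximation can be several points away from the power actually delivered.

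Two things are at stake. The first is the stated type II error, which is about half of what the test gives. The second is the decision itself. The verdict depends on whether 1, 2 or 3 events occur. With the count, the alpha and the scope of the Bonferroni correction all open, the same data could be called significant or not after they are seen.

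**Working it through.** **Inputs.** p0 = .031, p1 = .0047, one-sided alpha = .05, beta = .05, N = 231 (all section 9.2); direction p < p0 (9.1); final alpha .0492 (9.4.4).

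**1. Reproducing 231.** The arcsine formula is n = [(z_α + z_β) / (2·asin√p0 − 2·asin√p1)]². With z_α = z_β = 1.645, the denominator is .3540 − .1372 = .2168, so n = (3.290/.2168)² = 230.3, rounded up to 231. The normal formula using both variances gives 228.5, rounded up to 229. So 231 is the correct arcsine answer.

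**2. Rejection rule of the exact one-sided binomial test at N = 231.** Take the largest c with P(X ≤ c | 231, .031) ≤ alpha. Power is P(X ≤ c | 231, .0047).

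| Reject if events ≤ | Attained alpha (p = .031) | Power (p = .0047) |
|---|---|---|
| 1 | .0058 | .704 |
| 2 | .0247 | .904 |
| 3 | .0707 | .976 |

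Three events exceed both .05 and .0492, so the rule is 2 or fewer at either alpha. Power is 90.4% and beta is 1 − .904 = 9.6%. Over the rounding range of the two rates (p0 .0305 to .0315, p1 .00465 to .00475), power stays between 90.1% and 90.6%. An uncorrected z-test with the null variance gives p = .0250 for 2 events and p = .0571 for 3, which is the same rule.

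**3. If Bonferroni covers the primary test.**
- .05/2 = .0250 is above .02466, so the rule stays at 2 events.
- .0492/2 = .0246 is below .02466, so the rule drops to 1 event and power to 70.4%.
- .05/3 = .0167 also gives 1 event.
- At .0492 the 1-event rule holds for m = 2 to 8: .0492/8 = .00615 is above .00582, while .0492/9 = .00547 is below it.

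With exactly 2 events, the conclusion for m = 2 therefore depends on which alpha is divided.

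**4. If the as-treated number differs from 231 (alpha .0492).**

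| As-treated n | Reject if events ≤ | Power at .0047 |
|---|---|---|
| 152 to 201 | 1 | 83.9% falling to 75.6% |
| 202 to 248 | 2 | 92.9% falling to 88.7% |

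Against 231, n = 202 means 29/231 = 12.6% outside the as-treated set, and n = 201 means 30/231 = 13.0%. Power changes by a step at that point. The first n with exact power of at least 95% is 248 at alpha .05 and 249 at .0492.

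**5. Sensitivity to the assumed rate.** Section 9.2 gives no source for 0.0047, while it reports of the historical data "Rates of MI range from 1.9 to 8.8" percent. With the 2-event rule at N = 231, power is 59% at a true rate of 1.0%, 33% at 1.5% and 18% at 1.9%.

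**The case against.** The strongest reply is that 231 is not a miscalculation and that an exact test is nowhere named. Both are true. The number is the right answer from an approximation, and exactness is inferred from the formula printed in 9.4.2.

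Other one-sided versions would reject with 3 events at N = 231: arcsine (p = .028), likelihood ratio (.037), mid-p (.048) and Wald (.008). Power would then be 97.6%. So the 2-event rule does not hold for every conceivable test. But none of these versions is in the plan, and rejecting at 3 events carries a true type I error of 7.1%, above the stated 5%. In the other direction, 9.4.2 does not repeat the sidedness. A two-sided exact test gives p = .054 for 2 events, which leaves a 1-event rule and 70.4% power.

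It can also be said that the consequence is limited. This is a pilot, only 100 patients are approved so far, that number is stated not to be statistically based, and false-positive risk is not raised. This keeps the point from being more serious. It does not make the power statement correct, because 9.2 keeps 231 as the total if the trial continues.

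Finally, 9.2 replaces patients lost to follow-up but does not mention replacing those who cannot stop DAPT at 30 days, so the as-treated number may fall below 231. That is a reason to state the rule by n.

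**Conclusion.** The concern holds. On the plan's own inputs, the one-sided binomial test at N = 231 rejects with 2 or fewer events, with attained alpha 2.5% and power 90.4%. The stated beta of 5% is in fact 9.6%, and power is 4.6 points below the claim. The result is the same at alpha .05 and .0492. It rests on the exact one-sided reading of sections 9.1, 9.2 and 9.4.2, on 231 patients in the primary analysis, and on no Bonferroni adjustment of the primary test. Type I error is protected. The missing rejection count matters at least as much as the power figure, since the unsettled choices move the rule between 1 and 2 events and power between 70.4% and 90.4%. This should be corrected before the final analysis.

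**What to change.** Restate section 9.2 along these lines:

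> Exact one-sided binomial test of the composite primary endpoint at the final alpha of .0492. With 231 analysable as-treated patients, H0 is rejected if 2 or fewer events occur; attained alpha .025; power 90% at a true rate of 0.47%.

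In 9.4.2, say that the Bonferroni correction does not apply to this single primary test. If it does apply, give m and the resulting rule (at .0492, 1 or fewer events and power 70% for m = 2 to 8).

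Add the critical count by as-treated n at .0492: 1 or fewer for n = 152 to 201 (power 84% to 76%), and 2 or fewer for n = 202 to 248 (93% to 89%).

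It would also help to give the source of 0.0047 and, as sensitivity only, the power at 1.0%, 1.5% and 1.9% (59%, 33%, 18%).

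The cost is protocol wording. No extra patients are needed, because the table covers an as-treated number below 231. The downside is a less favourable stated power, 90% in place of 95%.

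### The power claim in section 9.2 rests on an unsourced 0.47% event rate: under the planned exact test, power at 231 patients is 90% at that rate, not 95%, and 18% at the lowest historic MI rate cited

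*Combined protocol and SAP*

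**What the plan says.** Section 9.2 plans a "one-sample binomial test with an alpha of .05 (one-tailed), beta of .05", takes a "constant proportion ( $p$ ) of .031" as the null value, and uses an "assumed primary endpoint proportion of 0.0047 resulting in a needed sample size of 231".

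The next paragraph of 9.2 gives the historical background: "Historic rates at 1-year follow up for ST showed variability ranging from 0.3 to 5.3" percent, then "Rates of MI range from 1.9 to 8.8" percent. It describes a time-to-event calculation for "sample sizes based on a 95% power determination resulting in a historic rate determination of 3.1" percent. So the 3.1% comparator has at least a described origin. The 0.47% has none, and 9.2 gives no sensitivity range around it.

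The primary endpoint in the synopsis (1.1) is the "Rate of cardiac death or myocardial infarction (SCAI definition) from 1 to 13 months post-index procedure", in patients eligible to stop DAPT at 30 days. Section 9.1 sets a one-sided alternative: the rate is lower than the standard-of-care rate.

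For the analysis, 9.4.2 says "The binomial test will be conducted to test the significance of deviations from the expected distribution" and prints the binomial probability formula. It sets alpha at .05, with a Bonferroni correction for multiple tests on the same sample. Section 9.4.4 reduces the final-analysis alpha to .0492. Section 9.4.2 plans no confidence interval.

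**The concern.** For a binomial endpoint, the assumed event rate fixes both the effect size and the variance under the alternative. Here it is the least supported input and the one on which power depends most. The endpoint includes MI, so in the same patients and window its rate cannot be below the MI rate. Yet 0.47% is about a quarter of the lowest MI rate that 9.2 quotes.

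If the true rate is well above 0.47%, a strategy that performs respectably will probably miss its test. The primary objective is safety, so a non-significant result could be read as a signal against 1-month DAPT when it shows only that the test had little power.

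**Working it through.** **Inputs.** p0 = .031, p1 = .0047, one-sided alpha .05, power .95 and N = 231 (9.2); lower-tail alternative (9.1); binomial test (9.4.2); lowest cited MI rate .019 (9.2).

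**Size of the assumed effect.** .0047/.031 = 0.15, an 85% relative reduction. .0047/.019 = 0.247, about a quarter.

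**The plan's own figure.** Arcsine formula: N = [(z.95 + z.95)/h]², with h = 2·arcsin√.031 − 2·arcsin√.0047 = .3540 − .1372 = .2168. Then N = (3.290/.2168)² = 230.3, rounded up to 231, which matches. The normal approximation with null and alternative variances gives 228.5, so 229.

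**Rejection region of the exact test.** With X ~ Binomial(231, .031):
- P(X ≤ 1) = .0058
- P(X ≤ 2) = .0247
- P(X ≤ 3) = .0707

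At one-sided .05 or .0492, the test rejects only at 2 or fewer events. The largest rejecting rate is 2/231 = 0.87%.

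**Exact power at N = 231**, P(X ≤ 2 | 231, p):

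| True rate | Origin of the rate | Exact power |
|---|---|---|
| 0.47% | plan's assumption | 90.4% |
| 0.67% | illustrative, about where power is 80% | 80% |
| 0.95% | illustrative, half of 1.9% | 62% |
| 1.9% | lowest historic MI rate in 9.2 | 18.4% |

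The two middle rates are not in the documents. Exact power at 0.47% first reaches 95% at N = 248.

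**Like for like by arcsine.** At 1.9%, h = .3540 − .2766 = .0774. Power = Φ(.0774·√231 − 1.645) = Φ(−.468) = 32%. The same formula gives 95.0% at 0.47%. So the fall from 0.47% to 1.9% is 90% to 18% (exact) or 95% to 32% (arcsine).

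**Sensitivity to alpha.** If the Bonferroni rule reaches the primary test with m = 2 and is applied to .0492, the threshold is .0246. P(X ≤ 2) is .02466, just above it, so the cutoff drops to 1 event. Power is then P(X ≤ 1): 70% at 0.47% and 6.5% at 1.9%. Applied to .05 it gives .025, and the cutoff stays at 2.

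**Exact one-sided 95% upper limits (Clopper-Pearson).** 2/231: 2.7%. 3/231: 3.3%. 4/231: 3.9%. Only the first is below 3.1%, in line with the 2-event cutoff.

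**The case against.** The strongest reply is that 1.9% to 8.8% are not this trial's rates. Section 9.2 draws on meta-analyses, a registry and ACS subsets. This trial excludes STEMI and NSTEMI indications, thrombus, left main disease, total occlusion and in-stent restenosis (5.2). It counts events only from month 1 to month 13, in patients eligible to stop DAPT, and those with an early MI, stroke, revascularisation or stent thrombosis are not to stop the P2Y12 inhibitor (7.1). The documents do not say whether the cited MI rates include the first month. The alternative in 9.1 is that the strategy does better than standard of care. All of this stands. A reader might infer that 0.47% is impossible because a composite cannot be rarer than its component. That rule holds only within the same patients and window, and the documents do not establish that match. High bleeding risk could push the rate the other way, and the plan does not settle the net effect.

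It is also fair that 231 follows from its stated inputs, so this is not an arithmetic error in N. The study is a hypothesis-generating pilot, its first 100 patients are expressly not sized statistically, and 231 depends on further approval. Missing the test with 3 or 4 events is correct behaviour against 3.1%, since the upper limits exceed it. And nothing in the plan says that failure to reject will be treated as harm; that misreading is a risk, not a stated rule.

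None of this supplies a source for 0.47% or a reason to state power at that rate alone.

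**Conclusion.** The concern holds in this form: 0.47% is unsourced, implies an 85% reduction from 3.1%, and lies below every MI rate cited beside it. Under the test that 9.4.2 names, the 95% power is not delivered even at 0.47% (90.4%). At the lowest cited MI rate, power is 18%.

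These powers assume that all 231 patients enter the primary analysis and that the final test is one-sided at .05 or .0492. Under the Bonferroni reading at .0246, they become 70% and 6.5%.

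Three stronger readings go too far:
- That power is 18% instead of 95%: this sets an exact figure against an approximate one, and treats a historic benchmark as the true rate.
- That 0.47% was borrowed from stent thrombosis: it lies inside that cited range (0.3% to 5.3%), but the plan does not say where it came from.
- That N must rise: the documents do not establish a true rate to size for.

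**What to change.** Leave N at 231.

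In 9.2:
- Replace the 95% power claim with exact power over a range: 90% at 0.47% and 18% at 1.9%, with 80% at 0.67% and 62% at 0.95% labelled as illustrative assumptions.
- State the source of 0.47%, or call it an optimistic scenario below every MI rate cited.
- Make the rejection cutoff conditional on the alpha actually used, and say whether the Bonferroni rule applies to the primary test.

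In 9.4.2:
- Report the observed primary rate with its exact one-sided 95% upper confidence limit beside the test.
- State that failure to reject is not evidence of harm.

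This needs changes of wording and one added interval, with no extra patients or procedures. The downside is a less favourable stated power.
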